### **5.7 Data Collection:**

#### **5.7.1 Patient-level data collection:**

Patient surveys: Patients will complete one brief pain assessment and one survey during the study period.

Baseline pain assessment: Patients will complete a baseline pain assessment at the time of enrollment using the Wong-Baker FACES pain rating scale (Appendix A). The patients will have been given the Wong-Baker FACES pain rating scale at the time of their initial clinic visit. They will be referred to this scale during the enrollment phone call, and baseline pain score will be recorded.

Post-procedural survey: Patients will also complete a brief survey (<10 minutes) after the radiotracer injection but before initiation of anesthesia (Appendix B). Patients should complete the survey within three hours of receipt of radiotracer injection. This will either occur in the nuclear medicine suite or in the preoperative holding area with an iPad device or paper/pen. This post-procedural survey has intentionally been kept brief to decrease patient burden, which is especially critical as it will be completed on the day of surgery.

Chart review: We will record information including: age, race/ethnicity, medical history of chronic pain or fibromyalgia (yes/no), history of prior breast and axillary procedures (biopsy, surgery), history of prior breast cancer, active narcotic or other pain medication usage (over the past week, use of narcotics including tramadol at least twice weekly and/or daily use of Tylenol, NSAIDs, gabapentin, and/or amitriptyline), breast cancer laterality, tumor histology, grade and size, clinical and pathologic AJCC 8th edition cancer stage, hormone receptor status (estrogen receptor, progesterone receptor, Her2neu), and receipt of neoadjuvant chemotherapy. Additionally, we will record any pain medications taken on the day of surgery prior to the arrival to nuclear medicine (narcotics, Tylenol, NSAIDs, gabapentin, amitriptyline), the time of lidocaine patch application, breast radiology procedure prior to nuclear medicine injection, and sentinel lymph node identification on pathology report. We will also record type of radiotracer received.

**5.7.2 Provider-level data collection:** Nuclear medicine staff surveys: Nuclear medicine technologists will be asked to complete two sets of surveys. Nuclear medicine faculty will be asked to complete the end-of-study survey only.

Post-procedural survey: The first survey will be to assess the nuclear medicine technologists' immediate perception of the ease of administration of the intervention and the patient's post procedural pain (Appendix D). Each post-procedural survey will be linked to the patient study ID. This will be completed by the technologist assisting with each enrolled patient.

Nuclear Medicine Technologists will be providing ancillary and/or standard of care services that are within their normal scope of clinical practice. As part of their normal scope of practice and standard of care, technologists assist Nuclear Medicine MD, DOs with radiotracer injections and associated pain control/pain mitigation procedures. Technologists who assist with study participants will be included in the study team.

End-of-study survey: We will also administer a brief survey at the end of the trial to the nuclear medicine faculty and technologists involved in the radiotracer injection and associated pain control for patients on the trial. The nuclear medicine faculty and technologists will be the staff most consistently involved in the injections throughout the study time period and therefore would be most reliably able to reflect on implementation of the interventions. (Appendix E).

Nuclear Medicine faculty are ultimately responsible for and supervise each radiotracer injection and associated pain control. They serve an integral role in the conduct of research-specific study procedures and are included in the study team.

## 5.8 Schedule of Events

	Time of new breast cancer diagnosis	First clinic visit with breast surgeon	Telephone call after first clinic visit & surgical scheduling	Following radiotracer injection	Following final surgical procedure	Following study accrual
Assess inclusion/exclusion criteria	X	X	X			
Introduce study, offer participation		X	X			
Verbal consent and authorization )		X	X			
Baseline pain assessment		X	X			
Post-procedural patient survey				X		
Assessment of sentinel lymph node identification via chart review					X	
Nuclear medicine staff questionnaire				X		X

## 7. MEASURES

*Primary patient outcome measure:* The Wong-Baker FACES pain rating scale is a standardized 10-point Likert scale that is validated and has utility for patients with lower health literacy (27,28). It has been used in prior studies assessing pain with radiotracer injection for SLN mapping (9–11) (Appendix A).

*Secondary patient survey outcome measures:*

- Short Form McGill questionnaire: This is a validated pain questionnaire taking an average of 2-5 minutes to complete that captures subjective experiences of pain in both sensory and affective categories on a 4-point Likert scale. A total score out of 45 is calculated with sensory and affective sub-scores (29) and has been used in prior studies assessing pain with radiotracer injection for SLN identification (9–11) (Appendix B).
- We will ask questions to determine whether the patient received their intervention as assigned (Appendix B).
- Questions to assess patient experience and satisfaction were drawn from the following:
  - Consumer Assessment of Healthcare Providers and Systems (CAHPS®) questions Surgical Care survey (30) (Appendix B).
  - The American Society of Anesthesiologists Satisfaction with Anesthesia Questions (31) (Appendix B).
  - Studies of patient experience/satisfaction with local analgesia using validated surveys (32–34)(Appendix B)
- Recommendation of topical anesthetic option: We will ask patients whether they would recommend the topical anesthetic option that they received to others (yes/no) and inquire why or why not (open ended)(Appendix B).

*Secondary staff outcome measures:*

- Intervention usability and perceived patient pain:
  - The question to assess intervention usability is adapted from the Single Ease Question developed for assessment of usability after the completion of a task (31). The question addressing perceived patient pain utilizes the Numeric Rating scale (NRS), a validated pain rating scale used previously in provider assessment of patient pain with radiotracer injection (2,32). (Appendix C)
- End of study assessment:
  - The goal of the survey will be to assess experiences with implementing each arm of the study and any identified barriers. Nuclear medicine providers will be asked to rank order the usability and perceived efficacy of the different interventions. Space will be provided for open ended comments on benefits or barriers related to the interventions. (Appendix D)

## 8. Statistical Considerations

### 8.1 Analysis

Data will be analyzed with intervention arms masked. All scales will be constructed in a manner consistent with scale development, including item non-response. We will compare mean post-procedural pain scores (primary outcome) and other continuous secondary outcomes with ANOVA, testing the null hypothesis that mean post-procedural pain scores will not statistically differ between the control and intervention arms. Pairwise differences between each of the intervention arms and the control arm will be assessed with t-tests. Differences in potential control measures between patients randomized to the control and intervention arms that arise by chance will be examined using a chi-square test or Fisher's exact test for categorical variables and analysis of variance (ANOVA) or Kruskal-Wallis test for continuous variables (depending on distribution), respectively. Should there be significant differences in control measures between arms, an analysis of covariance (ANCOVA) will be used to assess the primary outcome, including significant covariates. Differences in the secondary dichotomous measures (sentinel lymph node mapping, patient recommendation) will be assessed with Chi-Square analysis. We will summarize responses to open ended questions in the patient survey and adherence to intervention. All analyses will follow an intention to treat approach. We will summarize the responses from the nuclear medicine providers/staff to determine what arm was perceived to be the most effective method for pain control and the easiest to administer.

Secondary analysis will be performed on the type of radiotracer received and pain scores.

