## 1. Project Summary

We plan a randomized clinical trial comparing four user-friendly, non-invasive topical pain treatments, including a novel thermomechanical distraction technique, for breast cancer patients undergoing radiotracer injection for sentinel lymph node mapping. There is significant variability in how practices approach minimizing pain with radiotracer injection. Patients have identified this procedure as particularly painful out of all the procedures they undergo related to breast cancer treatment. To date, no best practice approach has been identified that is easily implemented into clinical workflows across practice types. Our objective is to identify a practical and widely adoptable solution to this persistent problem and improve the experience of breast cancer patients starting their treatment trajectory within the health system.

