##### **5.1 Study Overview and Schema**

This is a randomized clinical trial testing the effectiveness of four alternative approaches to topical anesthesia for radiotracer injections for women diagnosed with breast cancer undergoing sentinel lymph node mapping. We will test two types of topical anesthetic (ice and lidocaine patch) with and without the addition of a topical high frequency vibration device (always combined with cooling). Ice is our control group as it reflects current standard of care at our institution.

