### **5.5 Randomization:**

After consent for enrollment has been obtained and eligibility confirmed, patients will be randomized to one of four intervention arms. Patients will be stratified by whether or not they are scheduled to undergo a breast radiology procedure (eg. wire localization, seed localization, elucent clip) prior to nuclear medicine injection. Treatment group allocation will be communicated to nuclear medicine providers with a colored paper printout that travels with the patient on the day of surgery.

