### 8.2 Sample size

Power is calculated for our primary outcome variable, the Wong-Baker FACES pain scale. We assume patients randomly assigned to the control arm will have a Wong-Baker score consistent with scores reported for breast cancer patients in prior studies (mean=6.0, standard deviation=2.6) (10) and that the standard deviation across arms will be similar (2.6). A difference in 2 points in the Wong-Baker score between the standard care/control arm and the arm with the greatest reduction in pain score is considered clinically significant (27,37,38). A Monte Carlo power simulation of this one-way ANOVA design under an assumption of a sample with 40 patients per group, two point difference between usual care and the arm with the greatest difference, and alpha=0.05 yields 85% power to detect a difference of 2 points on the 10-point pain scale. Based on prior experience, we assume an enrollment rate of 60% (accounting for both declining to participate and drop-out after randomization) and plan to approach 270 patients and enroll 180 patients to allow for drop out to a target sample size of 160 patients.

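### The three arm-versus-ice t-tests have no multiplicity adjustment and no stated link to the ANOVA, so the error rate for naming an effective arm is not controlled; Dunnett's procedure would control it at about 85% power with no extra patients

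*Combined protocol and SAP*

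**What the plan says.** The trial has four arms: "patients will be randomized to one of four intervention arms" (section 5.5). Section 5.1 fixes the comparator, "Ice is our control group as it reflects current standard of care at our institution", and describes the design: "We will test two types of topical anesthetic (ice and lidocaine patch) with and without the addition of a topical high frequency vibration device".

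For the primary outcome, section 8.1 says "We will compare mean post-procedural pain scores (primary outcome) and other continuous secondary outcomes with ANOVA" and attaches the primary null hypothesis to that test: "testing the null hypothesis that mean post-procedural pain scores will not statistically differ between the control and intervention arms". The next sentence is "Pairwise differences between each of the intervention arms and the control arm will be assessed with t-tests". Nothing is said about multiplicity, the alpha for each comparison, sidedness, or whether the t-tests are read only after a significant F test.

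The only alpha in the plan, 0.05, is in section 8.2 and belongs to the ANOVA: "A Monte Carlo power simulation of this one-way ANOVA design under an assumption of a sample with 40 patients per group". The stated power is 85% for a largest difference of 2 points.

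**The concern.** The F test can show that the four means are not all equal, but it cannot say which arm differs from ice. Section 1 sets the aim: "Our objective is to identify a practical and widely adoptable solution to this persistent problem". The arm-versus-ice comparisons are what would point to a patch, a device or both. Their error rate as a family depends on a rule that the plan does not state. With three looks against one control, an unadjusted 0.05 per test allows more than a 5% chance of at least one false difference. Making the t-tests conditional on the ANOVA removes that excess when all arms equal ice, but not in every other pattern. At stake is a recommendation for or against a particular treatment that rests on a chance finding.

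**Working it through.** **Inputs.** Control mean 6.0, SD 2.6 in all arms, 40 per arm, largest difference 2 points, alpha 0.05 (section 8.2); three comparisons with ice (sections 5.1 and 8.1). Assumed because not stated: t-tests two-sided at 0.05 each, normal scores, all 40 per arm analysed. Mean patterns list ice first.

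**1. The plan's own figure.** One-way ANOVA power comes from the noncentral F with 3 and 156 df and λ = n·Σ(μᵢ − μ̄)²/SD². Section 8.2 does not give the two middle means, so several patterns were tried:
- 6/5/5/4: λ = 40 × 2/6.76 = 11.83, power 82.4%
- 6/5.5/5/4: λ = 40 × 2.1875/6.76 = 12.94, power 86.0%
- evenly spaced from 6 to 4: λ = 40 × 2.222/6.76 = 13.15, power 86.6%
- 6/6/6/4: λ = 40 × 3/6.76 = 17.75, power 95.2%

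The stated 85% is reproduced to within 2 points by the second and third patterns.

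**2. Error of the arm-versus-ice step.** Three independent tests would give 1 − 0.95³ = 14.3%. The shared control makes the tests correlated, so the rates were simulated (400,000 or more trials per pattern; repeat runs agree to about 0.1 point). The table gives the chance of at least one false difference from ice, in either direction. Gated means counted only if F is significant.

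| Means | F significant | Ungated | Gated | Dunnett |
|---|---|---|---|---|
| 6/6/6/6 | 5.0% | 12.5% | 4.0% | 5.0% |
| 6/6/6/5.5 | 12.2% | 9.1% | 4.4% | 3.5% |
| 6/6/6/5 | 38.6% | 9.1% | 7.0% | 3.5% |
| 6/6/6/4.5 | 74.8% | 9.0% | 8.6% | 3.5% |
| 6/6/6/4 | 95.2% | 9.1% | 9.0% | 3.5% |
| 6/4/6/4 | 98.9% | 5.0% | 5.0% | 1.9% |

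About half of each rate is a false benefit: with all arms equal to ice, 6.3% ungated, 2.0% gated and 2.5% with Dunnett; at 6/6/6/4, 4.5%, 4.5% and 1.8%. The gate stops protecting once a real effect in one arm makes F significant, because the two remaining null comparisons are then each tested at 0.05. Other patterns with a single arm equal to ice (6/6/4/4, 6/5/6/4) also stay at 5.0% to 5.1% on both readings.

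**3. Power for an arm 2 points better than ice.** Noncentrality = 2/(2.6 × √(2/40)) = 2/0.581 = 3.44.
- Unadjusted, critical value 1.991 (78 df): 92.5%
- Dunnett, critical value 2.372 (156 df): 85.6%, whatever the other means
- Bonferroni at 0.05/3: 84.5% from the same pooled model, 83.7% with two-sample tests
- Gated t-test: 81.9% (6/5/5/4), 85.0% (evenly spaced), 90.5% (6/6/6/4), 92.1% (6/4/6/4)

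The scale figure is not shown in the available text. If scores are rounded to whole numbers 0 to 10, Dunnett power is about 85%; if rounded to 0, 2, 4, 6, 8, 10, about 83%. The error rates are essentially unchanged.

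**4. Precision.** The 95% CI half-width for an arm-versus-ice difference is 1.991 × 0.581 = 1.16 points unadjusted and 2.372 × 0.581 = 1.38 points with Dunnett.

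**The case against.** The ANOVA is named first, carries the primary null and is the test that was powered. ANOVA followed by t-tests is a natural reading, and with all arms equal to ice it gives 4.0%, below 5%. Half of the false differences would show an arm as worse than ice and would not lead to its adoption. Under a gate, the excess is limited to two arms equal to ice with the third about 1 point or more better. Adjusting comparisons of separate treatments with one control is partly a matter of judgement, and it costs power.

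Much of this stands. It is why 12.5% is one end of a range and not the headline, and why the false-benefit rates are given beside it. But no gate is written, and a gate would not give strong control. The pattern that defeats it is plausible, because the arms share components and only the full combination might help. Shared components also favour treating the comparisons as one family.

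A further objection concerns the remedy. If the F test and Dunnett both stand at 0.05 with no stated roles, at least one of them rejects in 6.9% of trials when all arms equal ice. That is correct, so the replacement text must say what each test decides.

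A reader might go further and infer that the trial's primary test has a 12.5% false-positive rate, or that 160 patients are too few. The documents support neither. The single F test holds 5%, its 85% power is reproduced, and the plan does not say that the t-tests are ungated.

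**Conclusion.** The concern holds for the step that attributes a difference to a particular arm, and only there. On neither reading of section 8.1 is the family-wise error of the three comparisons held at 5% in all patterns. With all arms equal to ice it is 4.0% (gated) to 12.5% (ungated). With one arm alone better by 1 to 2 points it is 7% to 9% gated and about 9% ungated. With only one arm equal to ice there is no excess. False-benefit rates are about half of these.

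The figures assume 40 analysed per arm, a common SD of 2.6, normal scores and two-sided 0.05 per test. Dunnett's 5% applies to the arm-versus-ice family only. It was not simulated for the switch to ANCOVA, which section 8.1 triggers by significant baseline differences. The point is a cheap improvement; the primary analysis remains valid without it.

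**What to change.** In section 8.1, replace the t-test sentence with:

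> The overall F test is the primary test of any difference among arms. Claims that a specific arm differs from ice will rest only on Dunnett's procedure from the same model, two-sided family-wise alpha 0.05, with simultaneous 95% CIs. A significant F test alone will not support a claim for any arm, and Dunnett results will not replace the F test as the primary result.

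Stating an ANOVA gate alone would remove the ambiguity but would not give strong control. Bonferroni from the same model is an acceptable alternative, at about 1 point less power (84.5%).

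**Cost.** Wording only, with no extra patients. If ungated tests were intended, power for a 2-point difference falls from 92.5% to 85.6%. If gated tests were intended, the change runs from a gain of 3.7 points (6/5/5/4: 81.9% to 85.6%) through a loss of 4.9 (6/6/6/4: 90.5% to 85.6%) to a loss of 6.5 (6/4/6/4: 92.1% to 85.6%). Each interval widens from ±1.16 to ±1.38 points. Section 8.2 could also give the 85.6% as a figure separate from the ANOVA power, with its assumptions.

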### 8.2 Sample size

Power is calculated for our primary outcome variable, the Wong-Baker FACES pain scale. We assume patients randomly assigned to the control arm will have a Wong-Baker score consistent with scores reported for breast cancer patients in prior studies (mean=6.0, standard deviation=2.6) (10) and that the standard deviation across arms will be similar (2.6). A difference in 2 points in the Wong-Baker score between the standard care/control arm and the arm with the greatest reduction in pain score is considered clinically significant (27,37,38). A Monte Carlo power simulation of this one-way ANOVA design under an assumption of a sample with 40 patients per group, two point difference between usual care and the arm with the greatest difference, and alpha=0.05 yields 85% power to detect a difference of 2 points on the 10-point pain scale. Based on prior experience, we assume an enrollment rate of 60% (accounting for both declining to participate and drop-out after randomization) and plan to approach 270 patients and enroll 180 patients to allow for drop out to a target sample size of 160 patients.

## 9. Registration Procedures

Summary accrual information will be entered directly into the UW Paul P. Carbone Comprehensive Cancer Center OnCore database by the Study Coordinator.

A description of the clinical trial will be available on <http://www.ClinicalTrials.gov>, as required by U.S. Law.

## **10. Risks and Discomforts to Research Subjects**

### **Patients**

Adverse reaction to pain control modality: Patients will be excluded based on presence of lidocaine or other local anesthetic allergy/contraindication. However, it is still possible that a patient develops an adverse reaction to placement of a lidocaine patch. Patients may also have a skin reaction or discomfort associated with other intervention arms. Currently, if patients do not tolerate ice pack application (the standard of care at the institution), it can be promptly removed. Likewise, patients will be encouraged to communicate any discomfort or intolerance of intervention arm, at which time the intervention can be easily and promptly discontinued. We anticipate any skin reaction to be self-limited.

Loss of patient confidentiality: This risk has been minimized through data protection efforts. These include storing data sheets used to collect the clinical information and paper questionnaires in a locked drawer within a locked office when not utilized. Data will ultimately be transferred into a password protected database stored on the Department of Surgery server. Only individuals directly involved in the development and analysis of the research project will have access to the data. After transfer of information from the data sheet to the database, all data sheets will be destroyed. No direct or identifying PHI will be included in the final analysis or final manuscript. Patients who wish to sign electronic consent and receive an electronic copy of the signed consent will be educated regarding the security risks of transmitting information via email.

Distress from survey questions: It is unlikely that patients will experience distress associated with the pain assessment or satisfaction/experience questions. However, patients will have the opportunity to contact study staff regarding any concerns that arise related to the survey questions.

## **11. Records to be kept, Privacy, and Confidentiality**

All hard copy research files (including randomization lists, questionnaires, and data collection forms) will be kept in a secure, locked office in a locked filing cabinet and data will be transferred into a password protected computer and database stored on the Department of Surgery server. Only the minimum amount of patient and subject data that is necessary to achieve the aims of the research will be collected.

Patients: Directly identifiable information will not be collected on patient study questionnaires. To better protect patient information, electronic study data will be kept in two separate spreadsheets. The first spreadsheet will be a master code that includes the subject's name and medical record and an associated random study subject ID number. This subject ID will be kept in a password protected REDcap database on the Department of Surgery server (in a place separate from the data collection database). The data collection database will have the subject's ID number only, without subject (patient or provider) identifying information. When questionnaire data is then transferred into the database, only the subject ID will be included (no identifying information).

Only approved study personnel will have access to the identifiers (personnel approved for identification and recruitment and interaction with subjects will need access to update the master code/spreadsheet). Those who will not be interacting with subjects and/or who are only helping with analysis will only have access to the coded study data.

Nuclear medicine providers: Data from the nuclear medicine technologist post-procedure surveys will be linked to the patient subject ID. They will not contain additional patient-identifying information. These data will be stored on a password protected database on the Department of Surgery server.

After data analysis of the questionnaires is complete and the manuscript has been accepted for publication, all hard copies of research files will be destroyed. Other research materials and data are maintained in on the secure Department of Surgery server for a minimum of 7 years post publication. Data from this study will be stored for future research projects.

